8 STATISTICAL CONSIDERATIONS

8.1 RANDOMIZATION PROCEDURES

A combination of minimization and biased coin methodologies will be used to randomize participants to either DFO or placebo [Pocock 1975; Taves 1974]. The minimization method aims to control imbalance in the treatment groups with respect to pre-specified baseline characteristics; the biased coin approach is adopted to avoid deterministic assignment. Throughout the trial, the probability of treatment assignment will take into account the imbalance associated

with clinical site, baseline ICH score, OTT, baseline ICH volume, baseline NIHSS score, and concurrent use of anticoagulants at the time of ICH onset.

8.2 STUDY ENDPOINTS AND DATA ANALYSIS

8.2.1 CLINICAL ENDPOINTS

The primary efficacy outcome measure is the mRS, dichotomized to define good functional outcome as mRS score of 0-2 at 90 days. At the conclusion of the study, the proportion of DFO-treated subjects with a good outcome will be compared to the placebo proportion in a futility analysis. The primary futility hypothesis is tested via generalized linear model relating the probability of a good outcome to the treatment. Adjustment for OTT, ICH score, baseline ICH volume, NIHSS score, and anticoagulant use are included in the model to obtain proper significance due to the inclusion of these variables in the randomization scheme. The binomial distribution for Y , with the identity link, is used to derive an estimate of the adjusted risk difference for good outcome. The primary futility hypothesis, $H_0: (\pi_{DFO} - \pi_{placebo}) \geq 0.12$, will be tested at one-sided alpha (the probability that an effective intervention will be called ineffective, or futile) 0.10. The corresponding alternative hypothesis, $H_A: (\pi_{DFO} - \pi_{placebo}) < 0.12$, defines futility as a treatment effect less than absolute 12% in favor of DFO. The futility analysis will be conducted using a one-sided 90% upper confidence bound on the risk difference, which is consistent with the one-sided alternative hypothesis and stated level of significance. To declare futility, the entire interval must lie below the value 0.12, indicating that the true difference in risk of good outcome is less than 0.12 with 90% confidence. Under this design, a significant result would suggest that it would be futile to move DFO forward to Phase III testing.

As secondary analyses of the primary outcome, the presence of a differential treatment effect in the OTT windows will be explored. The generalized linear model described above for the primary analysis will be expanded to include an interaction between treatment and OTT window. While the Trial will be underpowered to definitively address this question, the magnitude of the treatment effect, and corresponding confidence interval, will be estimated for each time window. A dichotomized analysis considering the proportion of DFO- and placebo-treated subjects with mRS 0-3 will also be performed. Although mRS 0-3 is less favorable than the primary outcome of mRS 0-2, it would still be a desirable effect in patients with ICH given that no treatments exist to reduce disability. The trial is adequately powered to assess the futility hypothesis using mRS 0-3 as the outcome based on an absolute difference in treatment effect <13% in favor of DFO. We will also perform similar analyses at 180 days and ordinal analysis across all mRS scores as secondary outcome measures.

8.2.2 SAFETY ENDPOINTS:

All adverse events will be assessed until day-7 or discharge (whichever is earlier), and SAEs until day-90. Mortality (all causes and ICH-related) will be assessed until the end of the study (day-180). Safety endpoints of particular interest include all DFO-related adverse events until day-7 or discharge (whichever is earlier), all SAEs through day-90, and deaths (all causes and ICH-related) through day-180.

The following events will be defined as **ADVERSE EVENTS OF SPECIAL INTEREST** (AEOSI) for safety surveillance during this study: 1) Anaphylaxis (at any time point during study drug infusion); 2) Hypotension (defined as a decrease in blood pressure requiring medical intervention at any time point during drug infusion that cannot be explained by other causes); 3) Respiratory compromise of any cause during the in-hospital phase (day-7 or discharge, whichever is earlier); and 4) Development of new and unexplained visual or auditory changes after initiating treatment with the study drug.

All adverse events or complications will be submitted electronically via the WebDCU™ system and assigned to a system-organ class and preferred term using MedDRA coding dictionary. The number and percent of all adverse events will be summarized for each treatment arm by event type. Tables will be generated to detect any clinically significant laboratory abnormalities in change of values from baseline to end of the last infusion. We anticipate no missing safety data regarding adverse events, since patients will remain hospitalized and closely monitored until day-7 or discharge (whichever is earlier). The cumulative incidences of each AEOSI, as well as mortality, will be compared via 95% confidence intervals. Mortality will also be assessed via the log rank test for comparing survival curves.

Analysis of the safety data regarding the occurrence of ARDS will be carried out continuously throughout the trial by the unblinded study statistician, who will notify the EC and DSMB if recruitment must be stopped. The DSMB will be notified of each individual ARDS occurrence upon confirmation by the MSMs, per their request. Analysis of other safety data by the DSMB will occur semiannually (or more frequently if requested by the DSMB). If any of these analyses reveal serious emerging concerns, the EC, in consultation with the DSMB, may implement modifications to assure safety as necessary. Apparent, consistent and persistent evidence of net harm that tends to overwhelm any benefit may allow for premature termination of the study.

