4.1 Inclusion Criteria

- 1) Age ≥ 18 and ≤ 80 years
- 2) The diagnosis of ICH is confirmed by brain CT scan
- 3) NIHSS score ≥ 6 and GCS >6 upon presentation.
- 4) The first dose of the study drug is expected to be administered within 24h of ICH symptom onset (as described above).
- 5) Functional independence prior to ICH, defined as pre-ICH mRS ≤ 1 .
- 6) Signed and dated informed consent is obtained.

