4.3.2 SCREENING EVALUATIONS

The following clinical, laboratory, and radiological assessments will be carried out upon screening of potential study subjects: 1) Demographic data; 2) Medical history; 3) Review of medications; 4) General physical examination and vital signs; 5) Neurological examination, including visual auditory assessment, NIHSS, and GCS; 6) Review of head CT scans and chest x-rays; 7) Review of all inclusion/exclusion criteria; 8) Determination of ICH score and pre-ICH mRS score; 9) Laboratory tests (hematology, serum chemistries, serum albumin, coagulation parameters, renal and hepatic function tests and urine analysis).

A baseline pre-treatment plain (non-enhanced) brain CT confirming the presence of ICH is required to establish the diagnosis of ICH. The head CT should be reviewed by a Radiologist or a stroke-trained Neurologist experienced in the interpretation of CT scans. The need for additional diagnostic tests, such as CTA, conventional angiogram, or MRI/MRA to rule out secondary causes of ICH in suspected cases should be based on the judgment of the investigators according to the standards of clinical practice at each participating institution and the guidelines from the Stroke Council of the American Heart Association [Morgenstern, 2010; please refer to appendix II].

A baseline chest x-ray is required before enrollment to exclude the presence of bilateral pulmonary infiltrates or pulmonary edema.

A negative serum pregnancy test is required for all women of childbearing potential prior to enrollment into the study.

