8.4 SAMPLE SIZE CALCULATION

The sample size is calculated to achieve 80% power for the futility analysis described above using a one-sided alpha level of 0.10. It is anticipated that approximately 28% of control subjects will have mRS 0-2 at 3 months; this is based on the weighted average of the good outcome proportions reported in the placebo-treated subjects of the Factor VII, FAST, GAIN, and CHANT trials [Haley 2005; Lyden 2007; Mayer 2005-2008]. If the true good outcome proportions in the DFO and placebo arms are identical ($\pi_{tx}=0.28$, $\pi_{ctrl}=0.28$, a truly futile situation), 254 subjects (127 in each arm) are required to test the futility hypothesis with 80% power. This calculation takes into account the 0.12 null value specified in the futility hypothesis [Chow, 2003]. The primary analysis will be conducted according to a modified Intent-to-Treat (ITT) principle, wherein subjects in whom the study drug infusion is not initiated will be excluded from the analysis. Therefore, the final sample size was inflated by a factor of 1.11 (Friedman, Furberg, and DeMets) to account for dilution of the treatment effect associated with a conservative drop-out rate of 5% (due to loss-to-follow-up (LTFU) and

withdrawal of consent), and an additional factor of 1.04 to account for randomized subjects in whom the study drug is not initiated. Therefore, the final sample size is 294 subjects.

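### Age is known before randomisation but is not in the primary model; pre-specifying it is a cheap, optional gain in precision of unknown size

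*Protocol*

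**What the plan says.** Section 8.2.1 of the protocol tests futility with a binomial generalized linear model and an identity link, and sets a one-sided 90% upper confidence bound on the adjusted risk difference against 0.12. The covariates are given as "Adjustment for OTT, ICH score, baseline ICH volume, NIHSS score, and anticoagulant use". The reason offered is that these variables enter the randomisation scheme; precision is not mentioned. Section 8.1 lists the same five factors plus clinical site for the minimisation. Age appears in neither place.

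Age is nevertheless available for everyone. Section 4.1 makes it an eligibility criterion ("Age ≥ 18 and ≤ 80 years"), and the screening assessments in section 4.3.2 begin with "1) Demographic data; 2) Medical history; 3) Review of medications".

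On size, section 8.4 states: "The sample size is calculated to achieve 80% power for the futility analysis", "using a one-sided alpha level of 0.10". It takes no credit for covariate adjustment.

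**The concern.** Adjusting for a baseline variable that predicts outcome reduces the residual variance of the treatment comparison and removes the effect of any chance imbalance in that variable. The protocol's reason for its covariate list supports including those five variables but gives no reason for leaving out another baseline predictor. Elsewhere it accepts the principle: the exploratory analysis by ICH volume (sections 1.3 and 3.1) is to adjust for other variables that affect outcome.

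What is at stake is the width of the bound behind a go/no-go decision. If age carries prognostic information beyond NIHSS score, ICH volume and ICH score, some precision is left unused although the data are already collected. Age can be added credibly only before unblinding; added later, it would look data-driven.

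**Working it through.** **Inputs from section 8.4.** One-sided alpha 0.10; power 80%; "approximately 28% of control subjects will have mRS 0-2 at 3 months"; power evaluated where the arms do not differ ("If the true good outcome proportions in the DFO and placebo arms are identical"); margin 0.12 ("This calculation takes into account the 0.12 null value specified in the futility hypothesis"); 1:1 allocation (section 3.2).

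**Reproducing the plan's figure.** With unpooled variance, n per arm = 2 × 0.28 × 0.72 × (1.2816 + 0.8416)² / 0.12² = 126.2, rounded up to 127, or 254 in total. Inflation: 254 × 1.11 × 1.04 = 293.2, rounded up to 294. Both stated figures reproduce.

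**Baseline by that formula.** SE = √(2 × 0.28 × 0.72 / 127) = 0.05635. Half-width of the bound = 1.2816 × 0.05635 = 0.0722. Futility is declared when the observed difference is below 0.12 − 0.0722 = 0.048. Power = Φ(0.12/0.05635 − 1.2816) = 80.2%.

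**Adding age.** Let R² be the share of the outcome variance left after the listed covariates that age explains. The protocol gives no value, so R² is assumed over a range. Then SE is multiplied by √(1 − R²).

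The baseline above gives the five planned covariates no credit, so it is the power of an unadjusted comparison and not of the planned model. The last column therefore repeats the calculation with those five assumed, for illustration, to explain 30% of the variance: SE = 0.05635 × √0.70 × √(1 − R²).

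| Assumed R² for age | Half-width, unadjusted formula | Power, unadjusted formula | Equivalent N, 254/(1 − R²) | Power if the five covariates explain 30% |
|---|---|---|---|---|
| 0 | 0.0722 | 80.2% | 254 | 89.7% |
| 0.01 | 0.0718 | 80.5% | 257 | 89.9% |
| 0.05 | 0.0704 | 81.7% | 267 | 90.8% |
| 0.08 | 0.0693 | 82.6% | 276 | 91.5% |

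The largest gain in the table is 82.6 − 80.2 = 2.4 points from the unadjusted baseline and 91.5 − 89.7 = 1.8 points from the 30% baseline.

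**Chance imbalance.** Without an age term, an age imbalance of k standard errors moves the estimate by k × √R² × 0.0563. At R² = 0.05, one standard error moves it 1.3 points and two move it 2.5 points. At R² = 0.01 the shifts are 0.6 and 1.1 points.

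**Illustrative simulation.** This used n = 254, invented covariate distributions, 400 runs per setting and a linear risk-difference model. Log-odds slopes for age of 0, 0.2, 0.4 and 0.6 per decade changed the variance of the risk difference by about +0.5%, −0.6%, −2.9% and −7.1%. In the same runs a plain identity-link binomial fit failed to converge or gave fitted probabilities outside 0 to 1 in 97.5% to 99% of runs without age and in 98% to 100% with age. Those failure rates depend on the invented data and a simple fitting routine. They show only that the difficulty does not come from age.

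**The case against.** The strongest reply is that nothing here is wrong. The protocol states a rule for its covariates, namely that the randomisation factors go in. Age is not a randomisation factor, so leaving it out follows the rule. Further covariates are often settled in an analysis plan, which is not at hand. This stands as far as it denies an error. It does not remove the suggestion, because the protocol itself fixes the primary covariate list.

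The second objection is that no passage shows age to predict mRS 0-2 beyond NIHSS score, ICH volume and ICH score. This stands in full. A reader might infer from the 62-year eligible range that precision is certainly being lost, but an eligible range shows neither the spread that will be enrolled nor any prognostic value. How far the ICH score already carries age cannot be checked, since its appendix is not reproduced.

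A reader might also infer that chance age imbalance biases the result. It does not. Over repeated randomisation it is ordinary sampling variation, already reflected in the bound, and any part correlated with the listed covariates is adjusted for. The shifts shown above are conditional on a particular realised imbalance.

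Finally, the gain is not free: a further continuous term adds constraints on fitted probabilities under an identity link. That is fair, but the same weakness is present without age.

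**Conclusion.** A minor, optional improvement, not a defect. The sample size reproduces, the stated power is met without age, and the type I error rate is nominal. The documents do not support reading the omission as a shortfall in power: 80% is what the design promises before any adjustment, and the planned five-covariate model may do better.

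The benefit of adding age is roughly 0 to 2.5 percentage points of power, equivalent to at most about 22 subjects over the range examined, and it could be nil. This rests on an assumed residual R² of 0 to 0.08 and, for the second baseline, an assumed 30% of variance explained by the planned covariates. Confidence that the gain is material is low.

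**What to change.** Add age in years, as a linear term, to the pre-specified covariates of the primary model and of the mRS 0-3 and day-180 models.

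Before unblinding, also fix how the adjusted risk difference is obtained, in one of two ways:

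- use a logistic model with the same covariates from the outset and standardise it to a risk difference; or
- keep the identity-link model and name the trigger for moving to that standardised model: non-convergence, or fitted probabilities outside 0 to 1.

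A loosely worded fallback would leave the choice of primary estimator open to the data.

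The cost is a short change to the analysis text and no new data collection. The downside is one degree of freedom, plus one more continuous term in a model whose identity link can already fail to fit.

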8.5 LOSS-TO-FOLLOW-UP AND MISSING DATA

Extensive efforts will be made to keep missing data, particularly the primary outcome (mRS at 90 days), to a minimum, and to ensure near complete follow-up. Missing primary outcome data will be imputed via standard multiple imputation (MI) methods (i.e. via logistic regression model predicting outcome based on pertinent baseline and treatment data). As a sensitivity assessment, we will use the Last Observation Carried Forward (LOCF) approach, wherein the last available score will be carried forward for missing day 90 assessments. If the treatment effect is robust, we expect to reach similar conclusions via these imputation methods, particularly for minimal missing data (<5%).

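### The primary identity-link coefficient equals the difference in proportions only if risks are additive; under a constant odds ratio the stated 10% false-futility risk can rise to about 11-19%

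*Protocol*

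**What the plan says.** Protocol section 8.2.1 states the null as a difference in good-outcome proportions (DFO minus placebo) of at least 0.12. It tests this at a one-sided level of 0.10, defined as "the probability that an effective intervention will be called ineffective, or futile". The model is binomial and, "with the identity link, is used to derive an estimate of the adjusted risk difference for good outcome". On covariates it says: "Adjustment for OTT, ICH score, baseline ICH volume, NIHSS score, and anticoagulant use are included in the model to obtain proper significance". The rule is: "To declare futility, the entire interval must lie below the value 0.12".

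The same section extends the model to the onset-to-treatment (OTT) windows; it "will be expanded to include an interaction between treatment and OTT window". Section 8.1 gives the allocation method: "A combination of minimization and biased coin methodologies will be used to randomize participants to either DFO or placebo". Section 8.4 assumes 28% good outcomes on control and states that "254 subjects (127 in each arm) are required to test the futility hypothesis with 80% power". Section 8.5 adds: "Missing primary outcome data will be imputed via standard multiple imputation (MI) methods".

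Distribution, link, covariates, hypothesis and decision rule are therefore all fixed in the protocol. A statistical analysis plan that follows it would inherit the choice.

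**The concern.** A binomial model with identity link weights each patient by 1/(p(1-p)), where p is the fitted chance of good outcome. At a control rate near 28%, patients with a low chance count most. The hypothesis concerns the unweighted difference between arms. The two agree when covariates and treatment add on the risk scale. When they do not, the coefficient becomes a weighted average leaning towards low-chance patients, even in a converged fit with every fitted probability inside (0,1). More patients do not remove this.

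If low-chance patients gain less in absolute terms, the estimate is pulled down. A drug with a true 12-point benefit is then called futile more often than the protocol states. That is the error section 8.2.1 controls, in the trial's only go/no-go decision.

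**Working it through.** **1. The plan's own figures.** Inputs from 8.2.1 and 8.4: both arms 0.28, null value 0.12, one-sided 0.10, power 80%.
- n per arm = (1.2816 + 0.8416)² × 2 × 0.28 × 0.72 / 0.12² = 126.2, so 127 per arm and 254 in total.
- Power at 127 per arm = Φ(0.12/0.0563 − 1.2816) = 0.802.
- 254 × 1.11 × 1.04 = 293.2, so 294.

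The sample size reproduces and is not in question.

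**2. Direction of the pull.** Take two control risks from one simulated setting (AUC 0.62): 0.088 and 0.389.
- Weights: 1/(0.088 × 0.912) = 12.5 and 1/(0.389 × 0.611) = 4.2.
- Constant odds ratio, using the marginal value (0.40/0.60)/(0.28/0.72) = 1.71 for illustration: benefits of 0.054 and 0.133. The heavily weighted patients gain less, so the pull is downward.
- Constant proportional reduction in poor outcome, 0.60/0.72 = 0.833: benefits of 0.912 × 0.167 = 0.152 and 0.611 × 0.167 = 0.102. The pull is upward.

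**3. Size under a constant odds ratio.** Marginal rates 0.28 and 0.40 (true difference 0.12), 127 per arm, 4,000 trials per setting (Monte Carlo SE about 0.5 points). Assumed, not in the protocol:
- four dichotomised covariates: NIHSS, volume and OTT split 50:50, ICH score 38% high;
- latent correlation 0.5 among NIHSS, volume and ICH score;
- minimisation over 20 sites with coin 0.8;
- the prognostic AUC.

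An interior fit has every fitted probability inside (0,1); boundary fits were clipped in the all-trials row.

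| Assumed AUC | 0.60 | 0.65 | 0.69 | 0.72 |
|---|---|---|---|---|
| Large-sample limit of coefficient (truth 0.120) | 0.118 | 0.115 | 0.110 | 0.104 |
| False futility, identity link, all trials | 11% | 14% | 16% | 19% |
| False futility, standardised logistic, all trials | 10-11% | 10-11% | 10-11% | 10-11% |
| Trials with an interior fit | 98% | 92% | 81% | 68% |
| Identity link, interior fits only | 11% | 14% | 17% | 23% |
| Standardised logistic, same interior trials | 10% | 11% | 12% | 13% |

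A linear model with robust SE also gave 10-11% over all trials, so the binomial weighting causes the shift, not the risk-difference scale. At a true difference of 0, power was 82-84% for standardised logistic and 81-84% for robust linear.

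**4. How much is bias alone.** With SE = √((0.28 × 0.72 + 0.40 × 0.60)/127) = 0.059, the risk is Φ((0.12 − limit)/0.059 − 1.2816). Limits of 0.118, 0.115, 0.110 and 0.104 give 10.6%, 11.6%, 13.3% and 15.6%. The rest of the simulated excess is small-sample SE error and, in the interior rows, selection of trials.

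**5. Other effect patterns.**
- Constant 12-point effect on a logistic baseline: limit 0.120 to 0.118; 11-14% on interior fits.
- Additive risks: no bias; 11-12% on interior fits in this set-up. A separate simulation gave 10.4-10.6% over all trials with observed-information SE.
- Constant proportional reduction in poor outcome: limits 0.121-0.126, error 8.9-10.4% on interior fits; another run gave a limit of about 0.123 and 7-10% over all trials.

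**6. Stability.** Separately coded simulations, constant odds ratio, all trials:
- One gave 11.1 / 11.2 / 14.1 / 18.4% at AUC 0.59 / 0.65 / 0.69 / 0.73, with logistic at 9.4-10.6%.
- Another gave 11.0 / 13.5 / 17.8% at 0.61 / 0.67 / 0.74, with logistic at 9.8-10.8%.
- A third, with all five covariates and observed-information SE, gave 11.1-11.8% at 0.62 and 15.1-18.1% at 0.69-0.72. With expected-information SE these became 12.6-14.6% and 20.6-27.8%. At 282 patients (294/1.04 = 282.7) it gave 11.8% at 0.62 and 18.2% at 0.69 with observed information.

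**The case against.** The strongest reply is that the risk difference is collapsible, so under its own model the coefficient is exactly the quantity in the hypothesis. This stands: the weakness is sensitivity to misspecification, not a wrong estimand or an internal contradiction.

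Second, nothing in the protocol favours a constant odds ratio. Section 1.3 leaves dependence of the effect on ICH volume as an exploratory question, and the reverse pattern moves the error to or below 10%. This also stands, so the inflation is conditional. The same silence means the protocol gives no ground for additivity either.

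Third, size depends on prognostic strength, covariate coding and the type of SE. At AUC 0.60 the excess is only about 1 point. The simulations agree on direction and less closely on size. The main simulation omits anticoagulant use; adding 2% users left 36-57% of fits interior (AUC 0.72 down to 0.65), with error in those fits still 14-22%.

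A reader might infer a contrast of 17-24% against 9-11%. That mixes trial sets. The 17% and 23% come from interior fits, where logistic is itself 12-13%. The 24% comes from 2,000-trial runs with multiple imputation, 282 patients and 5% missing (identity 12 / 15 / 18 / 24%, logistic 11%). Over all trials with complete data the strong-prognosis contrast is 16-19% against 10-11%.

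A reader might also infer harm to the OTT-window analysis. Section 8.2.1 calls it exploratory and underpowered, so no decision turns on it. Failed or boundary fits may be handled in the statistical analysis plan and are no part of this point.

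**Conclusion.** The point holds as a conditional weakness in the primary estimator. If absolute benefit is smaller in patients with a low chance of good outcome, the false-futility risk exceeds the stated 0.10: about 11% at AUC 0.60, 14% at 0.65 and 16-19% at 0.69-0.72 over all trials under a constant odds ratio, against about 10-11% for standardised logistic. With a constant 12-point effect or additive risks it is close to 10-12% over all trials; with greater benefit in poor-prognosis patients it is at or below 10%.

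AUC, cut-points, correlations and effect pattern are assumptions. The documents do not show that the true risk is above 10%, only that the chosen model does not protect it. Changing the estimator is worthwhile because an alternative held about 10-11% over all trials in the patterns examined, at almost no cost. Confidence is medium: firm on mechanism and direction under the stated condition, less so on size.

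**What to change.** In section 8.2.1, make the primary estimator a logistic model with the same covariates, standardised to the marginal risk difference by averaging predicted risks over all analysed patients under each treatment. Compare its one-sided 90% upper bound, from the delta method or a bootstrap, with 0.12. A linear model with robust SE is an acceptable equivalent. Keep the identity-link fit as a sensitivity analysis. The OTT-window analysis may use the same estimator for consistency only.

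The cost is one sentence in the protocol and a few lines of code. The risk-difference scale, covariates, 0.12 threshold and sample size stay as they are, and the simulated power at zero effect stays above the planned 80%. The downside is that the SE is no longer read directly from a model coefficient.
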